3.1 General Design

The overall timeline for each subject's participation is indicated in Figure 1. Briefly, after randomization to treatment with TMS+CILT or sham TMS+CILT, all subjects will undergo baseline behavioral testing, neuroimaging, and genetic testing before receiving 10 treatment sessions over 2 weeks. Immediate post-treatment effects will be assessed within 4 days of the completion of therapy by repeating the baseline probes of treated and untreated stimulus sets from CILT. At 3 and 6 months after the completion of TMS, subjects will return for follow-up assessments during which the same tasks administered in Visits 1 and 2 will be repeated. Subjects who are able to undergo MRI scanning will have anatomic and fMRI scans at T5 and T22. Subjects who are not able or willing to undergo MRI will undergo CAT scan of the head.

Figure 1: Timeline for each subject

Screening Visit	Baseline 1	Baseline 2	Baseline 3	Baseline 4	Treatment 1-10	Follow-up 1	Follow-up 2 & 3	Follow-up 4, 5, 6
Visit 1	Visit 2	Visit 3	Visit 4	Visit 5	Visit 6-16	Visit 17	Visit 18-19	Visit 20-22
-Informed Consent	-WAB	-WAB	-Leftover Testing	-MRI/CAT scan	Real or Sham TMS (20 min, 1hz at 90% MT) + CILT	-CILT probe	3-months: -same as Baseline 1 & 2	6-months: -same as Baseline 1 & 2 -MRI scan
-Inclusion/Exclusion Criteria	-PNT	-Ruff Figural Pyramids and Fluency Test	-Baseline will continue into 4th and 5th visits if necessary					
-Demographics History	-Pyramids and Palm Trees	-Word and non-word repetition						
-Medical History	-Communication Confidence	-Cinderella Story						
-Medical Intake								
-Geriatric Depression Scale	Scale	-CILT baseline						
120 minutes	120-180 minutes	120-180 minutes	60-180 minutes	120 minutes	90-120 minutes	60 minutes	120-180 minutes	120-180 minutes

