7.3 Laboratory Evaluations

All subjects who have not had high quality brain imaging in the 3 months prior to entry to the project will undergo either MRI or CAT brain imaging at the University of Pennsylvania. MR examination will include structural imaging T1- weighted magnetization prepared rapid gradient echo (MP RAGE; TR=1620 ms, TE=3.08 ms; flip= 15; FOV = 280 x 280mm, 1.0 x 1.0 x 1.0 mm voxels; 160 slices); Coplanar T2 (TR=4010 ms, TE=76ms, flip=150, FOV=256 x 256 mm, slice thickness = 2.6 mm, 48 slices); T2 –weighted resting BOLD sequence (TR = 0.5s, TE = 30ms, 230x230 mm² FoV, 128x128 acquisition matrix) and a fast fluid attenuated inversion recover scan

or FLAIR (TR=9190 ms; TE=102 ms ; flip =180; FOV= 180 x 240; 1.3 x 0.8 x 4.0 mm; 40 slice) . We will also obtain diffusion imaging (HARDI; 2.5 x 2.5 x 2.5 mm voxels, 54 slices, 60 direction b-value=2500ms/mm²); and pseudo-continuous arterial spin labeling (pCASL; TR=4000 ms; TE=18 ms; 3.4 x 3.4 x 5 mm; flip angle 90; 16 slices, matrix=64 x 64). To avoid phase wrap artifact in subjects with large heads the slice thickness may be adjusted upwards slightly.

For subject unable or unwilling to undergo MRI imaging a high-resolution CAT (60 axial slices, 3mm thick, matrix =512 x 512) without contrast will be acquired.

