8.4.2 Identifying Predictors of Treatment Response

As in our primary analyses, we will use Linear Mixed Modeling (LMM) to identify the strongest clinical/linguistic predictors of response to TMS+CILT as compared to sham TMS+CILT from among variables like chronicity, severity, gender, depression severity, naming accuracy, apraxia of speech, core semantics, and sentence processing. Although we will be underpowered for formal tests of interaction given our moderate sample size, we will refit our primary endpoint model by adding interactions of the intervention indicator and potential predictors of response to therapy to see which are suggestive of differential intervention effects. We expect that these analyses will illuminate the clinical/linguistic predictors of treatment response, thereby defining the ideal “target population” for a future Phase 3 clinical trial.

Network Neuroscience measures of response to TMS+SLT

Subjects who can undergo MRI will have studies obtained prior to treatment and at 6 months after the completion of TMS. We will construct brain networks for each individual based on their baseline and post treatment BOLD fMRI data. We will use both the AAL (132) and Glasser et al. (40) parcellations and subject-specific lesion masks to exclude lesioned areas prior to atlas registration within each subject. Then, we will extract time series data from each region following modern preprocessing practices designed to reduce the influence of motion on BOLD time series (24). Across all pairs of region time series, we will compute wavelet coherence, which is well-suited for non-stationary data such as BOLD fMRI (128), to construct an adjacency matrix A that represents the pairwise coherence across all regions within the frequency band 0.01 to 0.10 Hz,

which is robust to physiological noise and evinces reliable functional network organization (44). We will constrain our analysis to the functional connections observed among regions identified to be involved in language processing (34) and their homotopic regions. Within each subject, we will compute a within-subjects t-test for elements (connections) in A₃ (final timepoint) versus A₁ (baseline) in the language and homotopic systems corrected for multiple corrections using a false discovery rate correction with a nominal corrected p-value of 0.05. This will allow us to detect the connections most modified by treatment and determine whether mechanism 1, 2, or 3 is supported.

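### The connectivity t-test is specified inside each subject, where each connection has one pre/post pair and no p-value; it should be run across subjects and compared between arms

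*Combined protocol and SAP*

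**What the plan says.** Section 2.2 makes the mechanism of TMS, studied by network analysis of imaging before and after treatment, a secondary objective. The only imaging test stated for it is in the network neuroscience part of Section 8.4.2.

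- **Scans.** "Subjects who can undergo MRI will have studies obtained prior to treatment and at 6 months after the completion of TMS". Section 3.1 agrees: "Subjects who are able to undergo MRI scanning will have anatomic and fMRI scans at T5 and T22". Section 7.3 lists one "weighted resting BOLD sequence" and gives no number of runs, scan length or time windows.
- **Data.** "We will construct brain networks for each individual based on their baseline and post treatment BOLD fMRI data". Wavelet coherence is computed for every pair of regions "to construct an adjacency matrix A that represents the pairwise coherence across all regions within the frequency band 0.01 to 0.10 Hz". Each scan thus gives one value per connection under a given parcellation.
- **Test.** "Within each subject, we will compute a within-subjects t-test for elements (connections) in" the final matrix (A3) against the baseline matrix (A1), limited to language regions and their counterparts in the other hemisphere, and "corrected for multiple corrections using a false discovery rate correction with a nominal corrected p-value of 0.05".
- **Purpose.** "This will allow us to detect the connections most modified by treatment and determine whether mechanism 1, 2, or 3 is supported".

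No group-level step and no TMS-versus-sham comparison of connectivity follows. Section 8.4.3 applies the same method to the AD sub-study, without lesion masks.

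**The concern.** A t-test needs replication of whatever it tests. The sentence places the test inside the individual, and an individual supplies one baseline value and one final value for each connection. A single difference has no spread, so there is no standard error and no p-value. The FDR step presupposes one p-value per connection and has nothing to act on.

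An analyst following the text would have to replace the stated unit of analysis before obtaining any result. The plan gives no guidance on the replacement: subjects pooled, one arm only, or one arm against the other. Those choices answer different questions, and the inference about mechanism is meant to rest on the result. Leaving the choice until the data are in hand removes the benefit of prespecification for this objective.

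**Working it through.** The plan gives no sample size or power figure for the connectivity analysis, so there is none to reproduce. The check has three steps.

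**1. The test as written**

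Inputs: one baseline and one final matrix per subject (Sections 3.1 and 8.4.2); one coherence value per connection per matrix (Section 8.4.2).

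- Pairs per connection inside one subject: n = 1.
- Degrees of freedom: n − 1 = 0.
- Variance of the difference: Σ(d − d̄)² / (n − 1) = 0/0, undefined.
- Running a paired t-test on one illustrative pair (0.4 and 0.3) returned 0 degrees of freedom and undefined t and p.

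**2. Does anything else in the text supply replication?**

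- *Repeat scans or runs:* none are described. Sections 3.1.3 and 6.4.4 add only the follow-up scan already counted.
- *Time windows within a scan:* none are defined, and the matrix is a single summary over the frequency band.
- *Two parcellations:* Section 8.4.2 uses two atlases, but they divide the same BOLD data in different ways and are not repeat measurements of a connection.
- *All connections of one subject treated as the sample:* this gives one p-value for the average shift of the network. FDR would have nothing to correct and no connection would be identified, so it conflicts with the correction step and with the stated purpose.

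**3. Can the planned scans support a test across subjects?**

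Inputs: 75 evaluable subjects (Section 8.3) allocated 2:1 (Section 3.1.4), so 50 TMS and 25 sham if all have usable scan pairs. The number able to have MRI is not given; 80% and 60% are shown as assumptions. The number of regions is not given; 10, 20 and 40 are assumed, and m = k(k − 1)/2 gives 45, 190 and 780 connections.

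- Between arms, one change score per subject: df = 50 + 25 − 2 = 73.
- Paired within the TMS arm: df = 50 − 1 = 49.

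As a check on the method, the noncentral t gives 80.5% power for 0.7 SD with 50 and 25 subjects, which agrees with the 80% in Section 8.3 for the WAB-AQ.

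Minimum detectable change at 80% power, two-sided, in SDs of the change score. The adjusted columns use 0.05/m, the smallest Benjamini-Hochberg threshold, and are therefore conservative.

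| Test | Subjects | Unadjusted 0.05 | m = 45 | m = 190 | m = 780 |
|---|---|---|---|---|---|
| Between arms | 50 v 25 | 0.70 | 1.04 | 1.15 | 1.25 |
| Between arms | 40 v 20 | 0.78 | 1.18 | 1.30 | 1.42 |
| Between arms | 30 v 15 | 0.91 | 1.38 | 1.54 | 1.69 |
| Paired, TMS arm | 50 | 0.40 | 0.61 | 0.68 | 0.75 |
| Paired, TMS arm | 40 | 0.45 | 0.70 | 0.78 | 0.85 |
| Paired, TMS arm | 30 | 0.53 | 0.83 | 0.93 | 1.02 |

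Sensitivity given up relative to a pooled pre/post test, in the same SD units: the standard error is √(1/50 + 1/25) = 0.245 between arms and 1/√75 = 0.115 pooled, a ratio of about 2.1. The pooled test answers a different question, because both arms receive CILT (Section 3.1) and any pre/post change mixes TMS with CILT, time and session effects.

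**The case against.** The best defence is that this is loose wording. A within-subjects t-test is a common name for a paired test with subjects as replicates. If the first three words of the sentence are removed, what remains is an ordinary paired test per connection, and FDR over connections fits that reading. This may well be what the authors meant. It stands as an account of intent and shows that the repair is small. It does not rescue the text, which names the individual as the place of the test and describes no later step across subjects. Even on this reading the arms are not compared, so change could not be attributed to TMS.

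A second defence is that wavelet coherence can be resolved over time and could give several values per connection within a scan. Nothing in Section 7.3 or 8.4.2 defines such values. Neighbouring windows would also be autocorrelated, so an ordinary t-test on them would not be valid.

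Two stronger readings are tempting. A reader might infer that the scans cannot yield a connection-level result at all. The documents do not support this: paired scans on many subjects are what a test across subjects needs. A reader might also infer that the plan will pool connections inside a subject and so produce inflated false-positive rates. The FDR step and the stated purpose rule that test out, so no error rate for it should be charged to the plan.

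It is also fair to say that the reach is limited. The only listed secondary endpoint is PNT naming accuracy (Sections 3.3.2 and 8.2), and no imaging measure is named as an endpoint.

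**Conclusion.** The point holds as a defect in how the test is specified. As written, each connection has one pair, 0 degrees of freedom and no p-value, so the FDR step cannot be carried out and the changed connections cannot be identified. This follows from the text alone and needs no outside figure. It applies to Section 8.4.2 and, by reference, to Section 8.4.3.

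The data to be collected are adequate in kind for a valid test: up to 73 degrees of freedom between arms if all 75 subjects have usable scan pairs. Such a test would reliably find only large effects on single connections, about 1.0 to 1.7 SD at the strictest FDR threshold over the assumed ranges for scanned share and number of regions. Those figures describe the repaired test and are not needed for the conclusion.

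The consequence is confined to the secondary mechanism objective. The primary WAB-AQ analysis in Section 8.4.1 does not use this test. The wording should be corrected before the imaging data are analysed.

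**What to change.** In Section 8.4.2:

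1. Delete the opening three words of the test sentence and state that the subject is the unit of replication.
2. For each subject and connection, compute the post-minus-pre change in coherence on a named, suitable transformed scale (Fisher z is one option).
3. Test each connection across subjects by comparing the change between TMS+CILT and sham+CILT, with FDR at 0.05 over connections. Say whether the FDR family is one parcellation or both.
4. Report paired pre/post tests within each arm as descriptive only.
5. Report the number of subjects contributing to each connection, since lesion masks remove different regions in different people. If a minimum number is required, fix it before the data are seen.

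Section 8.4.3 inherits the change; item 5 matters less there because lesion masks do not apply.

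**Cost.** Plan wording and routine analysis code, with no new scans. No per-subject significance map is produced, and the between-arm test is less sensitive than a pooled pre/post test. That loss is the price of attributing change to TMS.

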8.2	Subject Population(s) for Analysis	32
9	Safety and Adverse Events	32
9.1	Definitions	32
9.1.4	Adverse Event	32
9.1.5	Serious Adverse Event	32
9.2	Recording of Adverse Events	33
9.3	Relationship of AE to Study	33
9.4	Reporting of Adverse Events, Adverse Device Effects and Unanticipated Problems	33
9.4.4	Follow-up report	33
9.4.5	Investigator reporting: notifying the study sponsor	33
9.5	Unblinding Procedures	34
9.6	Stopping Rules	34
9.7	Medical Monitoring	34
9.7.4	Data and Safety Monitoring Plan	34
10	Study Administration, Data Handling and Record Keeping	35
10.1	Confidentiality	35

10.2	Data Collection and Management	35
11	Study Monitoring, Auditing, and Inspecting	36
11.1	Study Monitoring Plan	36
11.2	Auditing and Inspecting	36
12	Ethical Considerations	36
12.1	Risks	36
12.2	Benefits	40
12.3	Risk Benefit Assessment	40
12.4	Informed Consent Process / HIPAA Authorization	40
13	Study Finances	41
13.1	Funding Source	41
13.2	Conflict of Interest	41
13.3	Subject Stipends or Payments	41
14	Publication Plan	41
15	References	41
16	Attachments	54
17	Appendix	55
17.1	Magventure MagPro Manual	55

List of Abbreviations

AE: Adverse event

BAC: Biostatistics Analysis Center

CAT: Computerized Axial Tomography

CILT: Constraint Induced Language Therapy

DSMB: Data and Safety Monitoring Board

fMRI: Functional Magnetic Resonance Imaging

IFG: Inferior Frontal Gyrus

NAVS: Northwestern Assessment of Verbs and Sentences

PNT: Philadelphia Naming Test

PWA: Patients With Aphasia

SAE: Serious Adverse Event

SLT: Speech Language Therapy

TMS: Transcranial Magnetic Stimulation

WAB-(AQ): Western Aphasia Battery - (Aphasia Quotient)

Study Summary

Title	A Phase II, Randomized, Blinded Study of Transcranial Magnetic Stimulation and Constraint Induced Language Therapy for the Treatment of Chronic Aphasia
Short Title	TMS and CILT for Chronic Aphasia
IRB Number	831532
Phase	Phase 2
Methodology	Randomized, Blinded, Sham-Controlled
Study Duration	5 years
Study Center(s)	University of Pennsylvania
Objectives	
Primary: To determine if the combination of TMS and CILT is more effective than sham TMS and CILT as a treatment for chronic aphasia from stroke.
 
Secondary: To identify anatomic and behavioral predictors of response to treatment and the mechanism underlying the beneficial effect of the treatment.

Number of Subjects	75 subjects

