2.2 Secondary Objectives (if applicable)

- To determine the mechanism(s) by which TMS improves language function using modern techniques for network analyses of neuroimaging data collected before and after TMS and CILT.
- To identify the predictors of response to TMS, including using genetic analysis.

3 Investigational Plan

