8.4 Statistical Methods

8.4.1 Statistical Analysis of Primary Outcomes

Prior to analysis, the presence of outliers will be determined by examining descriptive statistics and graphical summaries of primary and secondary outcomes. As noted, the primary end-point will be the change in WAB AQ from the baseline for the treatment and sham groups. An intent-to-treat analysis will be performed using Linear Mixed Models for repeated-measures outcomes using outcomes at 3 and 6 months simultaneously. LMM is a regression-based approach that is suitable for repeated assessments, unlike generalized linear model regression. Additionally, unlike ANOVA, it is robust to missing data under the missing at random (MAR) assumption and sphericity assumptions. The primary outcome model will include change from baseline on the WAB AQ as the response and intervention, assessment end-point, and the interaction of intervention and end-point as fixed effects. The model will also include the baseline WAB AQ score as a predictor to increase efficiency and account for baseline imbalances in aphasia severity. A random intercept and end-point slope will be included to reflect between-subject heterogeneity in changes in WAB AQ scores. To examine possible bias in estimated intervention effects due to data missing not at random, sensitivity analyses, such as shared parameter and pattern mixture models, will be used. Secondary analyses will adjust for covariates that are imbalanced between intervention arms as well as demographic and clinical variables such as age, history of depression, lesion size, aphasia type, gender, and aphasia severity. In an exploratory analysis, we will evaluate whether there is a direct treatment effect on the WAB AQ that is not mediated by changes in response to CILT stimuli by further adjusting our primary outcome model for changes in CILT stimuli (67).

The statistical modeling of the secondary outcome (PNT) will involve similar analyses, but with items and participants modeled as random effects. Item-level response types will be analyzed separately (e.g., correct vs. incorrect; semantic error versus other response, etc.) to allow for determination of intervention effects specific to response type.

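### The imaging analysis in 8.4.2 has no language outcome and no TMS-versus-sham term, so it cannot show how TMS improves language

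*Combined protocol and SAP*

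**What the plan says.** **Objective.** Section 2.2 of the combined protocol and SAP lists as a secondary objective: "To determine the mechanism(s) by which TMS improves language function using modern techniques for network analyses of neuroimaging data". The Study Summary speaks of "the mechanism underlying the beneficial effect of the treatment", and the Introduction says much the same. Each statement ties brain change to language benefit and attributes that benefit to TMS.

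**Analysis.** The network part of 8.4.2 builds a coherence matrix for each subject under two parcellations and keeps language regions and their right-sided counterparts. It then states: "Within each subject, we will compute a within-subjects t-test for elements (connections) in" the final against the baseline matrix, corrected "using a false discovery rate correction with a nominal corrected p-value of 0.05". The conclusion drawn is: "This will allow us to detect the connections most modified by treatment and determine whether mechanism 1, 2, or 3 is supported". Section 8.4.3 carries this plan to the AD sub-study without the lesion masks.

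**Related analyses.** The interaction models earlier in 8.4.2 aim "to identify the strongest clinical/linguistic predictors of response to TMS+CILT as compared to sham TMS+CILT from among variables like chronicity, severity, gender, depression severity" and other behavioural measures; no connectivity measure is named. The one mediation-type analysis, in 8.4.1, has a behavioural mediator: "we will evaluate whether there is a direct treatment effect on the WAB AQ that is not mediated by changes in response to CILT stimuli".

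**The concern.** A claim about how TMS improves language needs two links: TMS changes the connection more than sham does, and that change goes with language gain. The planned test supplies neither. All subjects receive ten sessions of CILT, so a before-after change in connectivity could come from CILT, repeated testing or time. With no language score in the analysis, nothing shows that the change is related to improvement. Adding only an arm comparison would still leave the second link open.

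At stake is the reading of the mechanism objective. Followed as written, the plan would report which of three mechanisms is supported from data that, analysed this way, do not bear on language gain.

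**Working it through.** **1. Is a linking analysis planned anywhere?**

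| Place | Content | Connectivity change linked to language? | TMS vs sham on connectivity? |
|---|---|---|---|
| 8.4.2, network part | Final vs baseline connections, FDR 0.05 | No | No |
| 8.4.2, predictor models | Arm by clinical/linguistic predictor | No | No |
| 8.4.1, exploratory | WAB AQ adjusted for CILT-stimulus change | No (behavioural mediator) | No |
| 7.7 | Coding system that links sample data to outcomes | No (data handling, not a model) | No |
| 8.4.3 | As 8.4.2, without lesion masks | No | No |

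**2. Are the data there?** Yes. Section 8.4.2 has MRI before treatment and 6 months after TMS. The primary endpoint (3.3.1, 8.1) is WAB-AQ change over the same interval.

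**3. The plan's own power figure (8.3).** Inputs: 75 evaluable, 2:1 (50 TMS, 25 sham), difference 0.7 SD, alpha 0.05 (taken as two-sided). The noncentrality is 0.7/√(1/50 + 1/25) = 0.7/0.245 = 2.86, and Φ(2.86 − 1.96) = 81.5%. The t-based value is 80.5%. The stated 80% is reproduced. No power is given for imaging.

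**4. What a before-after test tells us.** Illustrative simulation with assumed values: 50 TMS and 25 sham; connectivity rises 0.5 SD equally in both arms; language improves 0.7 SD with TMS; the two are unrelated; 5,000 runs. The share significant at 0.05 was:
- before-after connectivity in the TMS arm: 93.7%
- connectivity change, TMS vs sham: 4.9%
- connectivity-language association adjusted for arm: 5.3%

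The first test is nearly always positive when both links are absent. It is a group-level analogue, because 8.4.2 does not say how within-subject results are combined.

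**5. What a linking analysis could detect.** The number with usable MRI is not stated; I assume 40 to 60 of 75. By Fisher z at 80% power, detectable r = tanh[(z₁₋α/₂ + 0.842)/√(n − 3 − k)], where k is the number of other model terms.

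- One unadjusted test (α = 0.05, k = 0): n = 40, tanh(2.802/√37) = 0.43; n = 60, tanh(2.802/√57) = 0.35.
- Three summaries with Bonferroni (α = 0.05/3, z = 2.394) and k = 4 (arm, baseline WAB AQ, lesion size, arm by connectivity change): n = 40, tanh(3.236/√33) = 0.51; n = 60, tanh(3.236/√53) = 0.42. Squared, these are about 26% and 18% of the variance in WAB-AQ change.
- Arm-specific slopes at n = 40 (about 27 TMS, 13 sham): tanh(2.802/√24) = 0.52 and tanh(2.802/√10) = 0.71.

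**6. Arm comparison of connectivity change.** Detectable standardised difference, one unadjusted test: 2.802 × √(1/27 + 1/13) = 0.95 at n = 40, and 2.802 × √(1/40 + 1/20) = 0.77 at n = 60.

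**7. AD sub-study.** With 30 subjects and no MRI loss, tanh(2.802/√27) = 0.49. With an assumed 20, tanh(2.802/√17) = 0.59.

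**The case against.** The strongest reply is that this is a secondary imaging aim in an MRI-capable subset, and that a linking model would have little power. Both statements are true. The arm-by-connectivity interaction is weaker still, and 8.4.2 itself concedes low power for interactions. This limits what the added analysis can claim. It does not justify choosing among mechanisms from a test without language or arm.

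A second reply is that mechanisms 1 to 3 may be defined, perhaps as connectivity patterns, in material not available here. That is possible. A reader might infer that the plan never defined them; the documents do not support counting that as an error. The point does not depend on the definitions, because a test without a language input cannot tie any connectivity pattern to language gain.

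A reader might also infer that the trial will announce a proven cause of language improvement. Section 8.4.2 says only that it will determine which mechanism is supported, and its test is specified within each subject, with no stated rule for combining subjects. Nor does it follow that the imaging data are unusable: the gap is in the analysis plan, not in data collection.

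**Conclusion.** The objective and the planned analysis do not match. As written, 8.4.2 can describe which connections changed. It cannot attribute the change to TMS or relate it to language gain, so it cannot address the objective in 2.2. This rests on the text alone.

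The power figures rest on the assumed 40 to 60 subjects with MRI, a two-sided alpha of 0.05 and three summaries. Under those assumptions only moderate to large associations (about 0.51 to 0.42) and large arm differences in connectivity change (0.95 to 0.77 SD before any multiplicity correction) are detectable. A null result would therefore not rule a mechanism out. The primary efficacy conclusion is unaffected. The plan should be changed, but nothing else in the trial depends on it.

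**What to change.** **Main study (8.4.2), labelled exploratory.** Name a few coherence summaries and one primary parcellation in advance. For each summary:
- (a) compare change from baseline to 6 months between TMS and sham, adjusting for the summary's baseline value;
- (b) regress WAB-AQ change from baseline to 6 months on change in the summary, adjusting for arm, baseline WAB AQ and lesion size, with arm by connectivity change as a descriptive term only.

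Call a mechanism of TMS supported only if its connections change differently between arms and that change is associated with WAB-AQ change. Report this as an association, not a causal effect. State the expected number with MRI and the detectable effects.

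**Alternative.** Narrow the objective in 2.2 and the Study Summary to describing connectivity change.

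**AD sub-study (8.4.3).** Use the same approach without lesion terms, descriptively only. First reconcile the scan time: 8.4.3 places the second scan at 6 months, while 3.2.3 and 6.4.5 place it with the 12-week follow-up.

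**Cost.** A short paragraph and a few extra models on data already being collected. The drawback is that the regressions relate two post-randomisation variables with limited power, so they cannot establish mediation.
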